#### 14.2. Documentation at the Trial Site

All data relating to the trial will be documented in the eCRF. This eCRF is developed to record the data requested by the protocol. The investigator will ensure the accuracy, completeness, legibility, and timeliness of the data recorded in the eCRFs.

Confidential Page 40 of 47

At the beginning of the trial, a site master file will be established at the investigational site. The investigator will maintain the trial documents as specified in the ICH Guideline of GCP and as required by the applicable regulatory requirements. The investigator will take measures to prevent accidental or premature destruction of these documents.

Prior to the start of the trial, a signature and delegation list will be completed showing the signatures and hand-written initials of all who are authorized to entry data or make corrections in the eCRF.

The investigator will permit trial-related monitoring, audits, and regulatory inspection, providing direct access to source data/documents.

## 14.3. Subject's Data and Data Protection

To protect the subject's identity, subject initials and a subject number will be assigned by the investigator to each trial subject and used in lieu of the subject's name when the investigator reports AEs and/or other trial-related data. Personal information will be treated as confidential but may need to be reviewed by authorized representatives of the CRO (monitor and auditor) and regulatory authorities. The subject's consent for direct access to his original medical records for data verification purposes has to be obtained prior to a subject's participation in the trial.

The investigator must maintain a list of names and identifying information (eg, initials, date of birth, subject identification code) of all subjects enrolled in the trial. The investigator will keep the subject identification code list in the site master file.

# 14.4. Data Management and Analysis

Data management based on GCP refers to the activities defined for achieving routines for entering subject information in a database in an efficient and error-free manner.

Data management routines include procedures for handling the eCRFs, database set up and handling, data verification, data validation, database quality control (QC), and documentation of activities performed, including information on discrepancies in the procedure.

Data Manager and Biostatistician from the CRO will perform the data management and analysis.

The initial notification of SAEs will be entered into the CROs safety database for coding, medical evaluation, and notification to the Health Authorities according to national regulatory requirements. Before clean-file, reconciliation will be performed between the two databases for all SAEs.

All data will be entered into the Oracle Clinical RDC system by site personnel. All data will undergo 100% source verification at the interim site visits by the monitor. In addition all data will undergo electronic edit checks and validation. Discrepant data will require resolution by the site personnel. The data will require Principal Investigator electronic signature at predetermined time points and at the end of each trial book. When the data for a subject are declared clean (all data entered, verified, validated and resolved) the case book will be frozen. At the close of the trial, after all data has been transmitted to the statistician for final analysis; the Sponsor will authorize final database lock.

Confidential Page 41 of 47

The QC of data will be performed to ensure that data entry and verification have been performed correctly in accordance to predefined instructions.

When the data have been entered, verified, and validated, the database will be locked for the analysis to start (Clean File).

#### 14.5. Amendments to the Protocol

The investigator will not implement any deviation from, or changes to the protocol without agreement by Sponsor and prior review and documented approval/favorable opinion from the IRB/IEC of an amendment, except where necessary to eliminate immediate hazards to trial subject or when the changes involve only logistical or administrative aspects of the trial (e.g., change in monitor(s), change in telephone numbers).

All changes or deviations of the trial must be confirmed in writing. Changes resulting in amendments will be made jointly between the CRO, the Sponsor and investigators. Amendments will be signed off in the same way as the protocol.

#### 14.5.1. Emergencies

When an emergency occurs that requires a departure from the protocol for an individual, a departure will be only for that subject. The investigator or other physician in attendance in such an emergency will, if circumstances and time permit, contact the following person immediately by telephone at:

Such contacts will be made as soon as possible to permit a decision as to whether or not the subject (for whom the departure from protocol was affected) is to continue in the trial. The eCRFs will completely describe the departure from the protocol and state the reasons for such departure. In addition, the IRB/IEC will be notified in writing of such departure from protocol.

#### 14.5.2. Protocol Violations/ Deviations

Protocol violations may be defined as divergences from the inclusion and exclusion criteria, concomitant medication restrictions, and any other protocol requirement that results in a significant added risk to the subject or has an impact on the quality of the data collected or the outcome of the trial. A subject may, but is not required, to be withdrawn if it is discovered that he/she committed a protocol violation during the course of the trial. Protocol waivers will be allowed on a case-by-case basis by the Sponsor's project manager and the waiver will be documented.

A protocol deviation may be defined as an occurrence when there is non-adherence to trial procedures or schedules as specified by the protocol that does not involve inclusion/exclusion criteria or the primary endpoint and that does not place the subject at any added risk or affect the

Confidential Page 42 of 47

data quality or trial outcome. Examples of "deviations" may include common out-of-window visits, a missed procedure, etc. A subject may not have to withdraw if the deviation is discovered during the course of the trial; this decision will be made by the investigator in conjunction with the Sponsor.

Protocol violations and deviations will be recorded on the appropriate eCRF page and tracked in a protocol violation and deviation log. The Medical monitor and Sponsor (or designee) should also be made aware of all protocol violations. Protocol violations and deviations must be reported in the final clinical trial report.

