## 8.2. Inclusion Criteria

Subjects are required to give written consent to participate in the trial. They will be informed that their primary medical practitioner and physiotherapist may be contacted to inform them of the trial and its conditions. Subjects must meet all entry criteria listed below.

- 1. Willingness to participate and give written informed consent
- Men and women ≥ 18 years of age
- 3. Sexually active women who are of child bearing potential will practice an acceptable method of birth control for the duration of the trial as judged by the investigator. Examples of acceptable contraception are: condoms, foams, jellies, diaphragm, intrauterine device, oral or long acting injected contraceptives, bilateral tubal ligation, bilateral oophorectomy, hysterectomy, or having a partner who is incapable of initiating conception. The practice of contraception must have started at least 3 months prior to trial entry.
- 4. If female, negative pregnancy test result at Screening
- 5. Diagnosed with MS and a known history of spasticity
- 6. Completed the double-blind randomized withdrawal phase (Part 3) of trial CLR\_09\_21 with no major protocol violation

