#### 8.3. Exclusion Criteria

Subjects will be excluded from the trial if any of the following exclusion criteria apply prior to enrollment:

- 2. History of alcohol abuse or use of recreational drugs within 12 months prior to Visit 1
- 3. History of chronic use of concomitant medications in neurologic or psychiatric illness which would affect the assessment of the safety of the trial medication
- 4. If the investigator feels that participation in this study is not in the best interest of the subject.

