5. STATISTICAL ANALYSIS GENERAL CONSIDERATIONS

5.1 Analysis Populations

5.1.1 Safety Population

The safety population will be all subjects who received at least one dose of Baclofen ER Capsules (GRS) during the study and have a subsequent contact with the clinic. Within the Safety Population, the following Safety Groups will be used for all summary and analysis purposes, in addition to an overall summary, derived from the three distinct sources (see Section 5.1.2):

[figure not shown]
- Safety Group 1: Subjects who completed CLR 09 21
- Safety Group 2: Subjects who are on entry
- Safety Group 3: Subjects Entering the Trial with no Prior Treatment

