6.1.3 Protocol Deviations

A protocol deviation is any change, divergence, or departure from the study design or procedure defined in the protocol.

A subset of the protocol deviations can be identified as a major protocol deviation as described below:

Major Protocol Deviation: A major protocol deviation that might significantly affect the completeness, accuracy, and/or reliability of the study data or that might significantly affect a subject's rights, safety, or well-being. Important deviations include includion/exclusion criteria violations, cases where withdrawal criteria developed but the subject was not withdrawn, receiving the wrong treatment or incorrect dose, and receiving excluded concomitant medications.

Upon soft lock of database, all documented protocol deviations in the study will be reviewed to identify all important protocol deviations by a data review team including representatives from clinical operations, medical, data management, and statistics, and sent to the sponsor for approval. Final decisions will be documented and databased.

Protocol deviations will be listed by subject with major deviaitons flagged.

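### Protocol 14.5.2 lets the Sponsor's project manager grant waivers without stated limit, which conflicts with the IRB/IEC approval rule in 14.5 and with the mandatory entry criteria

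*Protocol*

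**What the plan says.** The waiver provision is a single sentence in Protocol 14.5.2: "Protocol waivers will be allowed on a case-by-case basis". It gives the decision to the Sponsor's project manager and asks only that the waiver be documented. It closes a paragraph that opens with the definition "Protocol violations may be defined as divergences from the inclusion and exclusion criteria, concomitant medication restrictions, and any other protocol requirement", the last of these being limited to requirements whose breach adds significant risk or affects data quality or outcome. Minor deviations have their own paragraph, which contains no waiver provision.

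The parent section, 14.5, says the investigator will not implement a deviation or change "without agreement by Sponsor and prior review and documented approval/favorable opinion from the IRB/IEC of an amendment". It names two exceptions: removing an immediate hazard to a subject, and changes that are purely logistical or administrative.

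The eligibility text is unconditional. Section 8.2 states "Subjects must meet all entry criteria listed below". Section 8.3 states "Subjects will be excluded from the trial if any of the following exclusion criteria apply prior to enrollment". Section 10.3 has the investigator verify at Baseline that every criterion is satisfied, and 11.1 places enrolment after confirmation of eligibility. None of these sections mentions waivers.

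On reporting, 14.5.2 requires violations and deviations to be recorded in the eCRF, tracked in a log and reported in the final trial report. It adds that the medical monitor and Sponsor should be told of all violations. SAP 6.1.3 states "Important deviations include includion/exclusion criteria violations, cases where withdrawal criteria developed but the subject was not withdrawn" and plans a by-subject listing with major deviations flagged. It says nothing about waivers.

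**The concern.** A site reading 14.5.2 could ask the project manager for permission to enrol a subject who fails a criterion, receive it in writing, and believe the protocol had been followed. The same site reading 14.5 would conclude that this permission is not enough, because no IRB/IEC had approved an amendment and neither exception applies.

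The entry criteria include protections as well as definitions of the population. Among them are a negative pregnancy test, no recent alcohol abuse or recreational drug use and, in the synopsis, no history of hypersensitivity. A route around them that needs no prior medical or ethics review weakens those protections. It also means that the criteria printed in the report may not describe everyone who was knowingly admitted. Long-term safety is this trial's sole objective, so an accurate account of who was exposed matters.

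**Working it through.** No figure in the plan bears on this point and no arithmetic applies. The check is a side-by-side reading.

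**Step 1. What each route requires.**

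| Route | Sponsor agreement | Prior IRB/IEC approval | IRB/IEC notified |
|---|---|---|---|
| Deviation or change (14.5) | Required | Required, as an amendment | Through the approval |
| Immediate hazard, or logistical/administrative change (14.5) | Exempt | Exempt | Not stated in 14.5 |
| Emergency departure for one subject (14.5.1) | Telephone contact if time permits | Not required | Yes, in writing |
| Waiver (14.5.2) | Project manager decides | Not mentioned | Not mentioned |

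A project manager's waiver supplies at most the Sponsor's agreement, which is one of the two conditions in 14.5. A waiver decided in advance for a particular subject is not the removal of an immediate hazard. If it concerns an entry criterion, it is not logistical or administrative either. It therefore fits neither exception. As written, a planned waiver also carries less ethics oversight than an emergency departure, for which 14.5.1 requires written notice.

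**Step 2. Whether the waiver sentence reaches entry criteria.** It does not name them, so this is an inference. Three features support it. The sentence carries no restriction. It belongs to the paragraph on violations, whose first-named example is a departure from the inclusion and exclusion criteria. The paragraph on minor deviations, where a harmless waiver might be expected, has no such provision. Waivers therefore attach to the more serious class.

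**Step 3. Comparison with the eligibility text.** Sections 8.2 and 8.3 are absolute, and 10.3 asks the investigator to be certain. Section 11.1 is softer in form but has the same effect, since a subject with a waived criterion has not had eligibility confirmed. A waiver of an entry criterion is inconsistent with all four.

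**Step 4. Whether the analysis is affected.** Both documents define the safety population as subjects dosed at least once with later clinic contact (Protocol 12.2.1, SAP 5.1.1). Eligibility plays no part in that definition. No per-protocol set is defined, and SAP 5.2 describes the presentations as descriptive. A waived subject stays in every safety table, exactly as an unwaived violator would.

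**Step 5. Whether a waiver would be visible.** The SAP plans Listing 16.2.1.1 (eligibility), Listing 16.2.2 (deviations) and Table 14.1.1.2. As described, none of them separates a subject admitted with permission from one admitted by site error.

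**The case against.** The strongest reply has three parts. First, the waiver sentence directly follows the statement that a subject found to have a violation during the trial need not be withdrawn. It could therefore mean only that such a subject may continue. Second, 14.5.2 is a subsection of 14.5 and nothing in it disapplies the parent, so a waiver may be no more than the Sponsor's half of the approval. Third, the section does provide oversight through the eCRF record, the log, the final report and notice to the medical monitor.

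The first reading is possible but is not stated, and the sentence is not confined to it. The second would leave the sentence with almost no function, because Sponsor agreement is already required by 14.5. If it is what was meant, the protocol should say so. The third is correct and should be acknowledged, but telling the medical monitor is notification and not approval.

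A reader might also infer more than the text supports:

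- **That no entry criterion binds.** Sections 8.2, 8.3, 10.3 and 11.1 remain mandatory text. The problem is a conflict between sections, not the absence of rules.
- **That the SAP contradicts itself by flagging a waived subject as a major deviator.** A waiver does not make a subject eligible, so the flag is proper reporting. Under SAP 6.1.3 the classification also follows data-team review and Sponsor approval.
- **That a subject waived on completion of Part 3 has no safety group.** SAP 5.1.1 reads "Safety Group 1: Subjects who completed CLR 09 21", but the heading of 5.1.2.1, to which it refers, speaks of subjects who exited that study. That mismatch in wording exists with or without waivers.
- **That a particular number of subjects is affected.** The documents give no waiver rate or cap, so any count would rest on an arbitrary assumption.

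**Conclusion.** The conflict with 14.5 is plain on the text. The conflict with the eligibility sections rests on reading an unrestricted sentence, placed in the paragraph on violations, as covering the violations defined there. That inference is strong, but it remains an inference.

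The consequence is for subject protection, IRB/IEC oversight and the accuracy with which the enrolled population is described. The statistical consequence is small: no population definition or denominator rule changes, and no hypothesis test depends on eligibility. No numerical size can be given from the documents.

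This should be fixed. A reader might rank it among defects that invalidate the analysis, and the documents do not support that. It is still more than missing detail, because the sentence changes what sites and the Sponsor may consider themselves permitted to do.

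**What to change.** In Protocol 14.5.2, delete the waiver sentence. Alternatively, replace it with a statement that inclusion and exclusion criteria cannot be waived and that any intended exception follows 14.5, including prior IRB/IEC approval. The hazard exception in 14.5 and the emergency provision in 14.5.1 stay as they are.

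In SAP Listing 16.2.2, add a label for any waiver already granted, naming the criterion or requirement waived, and disclose such waivers in the trial report. The SAP is dated October 2017 and the protocol amendment it cites is dated December 2015, so enrolment may already be finished; the documents do not say. If it is, the label and the disclosure are the parts that can still be acted on.

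The cost is one protocol sentence and one label in a listing that is already planned. The downside is that a few borderline subjects may not be enrolled.

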# 15. QUALITY CONTROL AND QUALITY ASSURANCE

The investigator and the trial monitor (or designee) will to ensure that the trial staff receives appropriate training and that any information relevant to the conduct of this trial is forwarded to other staff as appropriate.

Quality assurance and quality control systems are implemented and maintained using written SOPs to ensure that the trial is conducted and data are generated, documented (recorded), and reported in compliance with the protocol, GCP, and the applicable regulatory requirement(s).

Quality control will be applied to each stage of data handling to ensure that all data are reliable and have been processed correctly.

Sponsor or designee at the end of the trial may conduct an internal or external audit. In such an instance, the auditor will be allowed direct access to the source medical records, the eCRFs, and the Site's master file for the trial.

Regulatory authorities worldwide may also audit the investigator during or after the trial. The investigator should contact the Sponsor immediately if this occurs, and must fully cooperate with regulatory authority audits conducted at a reasonable time in a reasonable manner.

#### 16. ETHICS

Before initiation of the study, Sponsor will seek permission from the regulatory authorities for conducting the trial. All documents required by the appropriate authorities will be submitted. Any notification/submission will be dated and contain sufficient information to identify the protocol.

# 16.1. Independent Ethics Committee (IEC) or Institutional Review Board (IRB)

This study will be initiated after the protocol is reviewed and approved by the appropriate IRB/IEC. The approval should be kept on file in the site master file with a copy in the Sponsor's file at the CRO.

Confidential Page 43 of 47

#### 16.2. Ethical Conduct of the Trial

This study will be carried out in conformity with GCP described in Guideline E6 of the ICH. This trial will also be carried out in conformity with the laws, rules, and regulations prevailing in the state and country of the investigational site.

# 16.3. Subject Information and Consent

Subjects will be screened and included in the study only after giving them adequate and appropriate information, and obtaining a written informed consent. The subject will be given sufficient time to consider the trial's implications before deciding to participate. The subject will be provided with a copy of the signed informed consent form. The confidentiality of the subject's records will be maintained.

Should there be any amendments to the final protocol, such that would directly affect the subject's participation in the trial, eg, a change in any procedure, the ICF will be amended to incorporate this modification and the subject must agree to sign this amended form indicating that they re-consent to continue their participation in the trial.

The investigator is responsible for obtaining the subject's freely given written consent, including date, and thereafter sign and date the consent form by her/himself before any trial related procedure is performed.

#### 17. DATA HANDLING AND RECORD KEEPING

The investigator must maintain all documentation related to this trial. Essential documents (as defined in the ICH Guideline for GCP) must be retained until at least 5 years after the last approval of a marketing application in an ICH region, and until there are no pending or contemplated marketing applications in an ICH region or at least 5 years have elapsed since the formal discontinuation of clinical development of the investigational product. These documents must be retained for a longer period, however, if required by the applicable regulatory requirement(s) or if needed by Sponsor.

In any case, all trial records such as but not limited to eCRFs, regulatory documents, the subject identification code list, subject files and other source data that support eCRFs must be retained for at least 15 years after the completion or discontinuation of the trial. If the investigator retires, relocates or for other reasons withdraws from the responsibility of keeping the trial records, custody must be transferred and Sponsor notified in writing.

Sponsor will notify the investigator in writing when the trial-related records are no longer needed.

Confidential Page 44 of 47

#### 18. FINANCING AND INSURANCE

The Sponsor is covered by a liability insurance that also covers liability towards subjects in clinical trials. Sponsor is covered by a General and Products liability insurance that includes clinical trials.

[figure not shown]
